## **7.7. Interim Analyses**

No interim analyses are planned for this study.

## **8. Safety**

Adverse events and birth outcomes will be the only safety data that will be reported.

### **8.1. Adverse Events**

Safety data will include the number of adverse events, classified as to category. Categories of events are based on the Medical Dictionary for Regulatory Activities (MedDRA). In addition to the type of event, adverse events will be categorized by severity, whether the adverse event is related to the study products/procedures, and whether the adverse event is expected.

Summary frequencies will be provided based on the overall number of events as well as separately by dose condition. In addition to the number of events of a particular type recorded, the percent of adverse events will be computed with the denominator being the number of participants in the safety population. Thus, the description of events will be reported as events/person. Categorization of the severity of events, relationship to study product/procedures, and expected nature of the event will be also reported as the frequency and percent of participants.

Safety analyses will be reported only to the DSMB and the appropriate Institutional Review Boards, with the exception that any serious adverse event will also be reported to the study sponsor.

Birth outcomes will be reported descriptively.

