Once participants have received the necessary equipment to complete the physiological portion of the screening, the research assistant will initiate a video call with the participant. During this call, the participant will be instructed on how to use the equipment and then will be asked to use the equipment to obtain the following physiological readings: breath CO levels, blood pressure, and heart rate. Participants will also be asked to collect a urine or saliva sample during the visit. If a saliva sample is collected, the participant will provide the saliva sample over video while the staff observes. If a urine sample is collected, staff will ask the participant to bring this urine sample to the video screen after collection to perform urinary cotinine, toxicology, and pregnancy tests. The participant will obtain the physiological readings and perform the tests and then will hold the results of the test up to the camera so that staff can interpret and record the readings on REDCap. Participants will also be instructed to have a pack of their usual brand cigarettes and all prescription medications they are currently taking to show to research staff.

A participant must complete her two-part screening session within 30 days of completing the pre-screening questionnaire. If the participant is not able to complete the two-part screening visit in that timeframe, she will need to complete the pre-screening questionnaire again. Participants will be reminded to engage in their normal activities and smoking practices prior to the screening visit.

Informed Consent Process:

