Before beginning the informed consent process, potential participants will need to produce identification as described above. The interviewer will confirm the age and identity of the participant. If the participant is not between the ages of 21 and 44, she will be dismissed without payment. During the first portion of the screening session, study information will be presented and documentation of the participant's informed consent via electronic signature on REDCap will be required prior to participating. In order to ensure adequate informed consent, participants will be asked to read the first several lines aloud (to determine literacy) and will then be given ample time to read the consent document. If the interviewer suspects the participant is not literate, he or she will have them continue reading further to confirm. Inability to read and comprehend written study materials will result in ineligibility and the interviewer will inform the participant that they are not eligible. Only after the participant and the researcher are fully satisfied that the participant understands the purpose of the study, the confidentiality of the data, the procedures, the risks/benefits and her rights as a research participant will the consent form be signed and the participant undergo screening procedures.

Screening Measures

Those who consent will be screened for eligibility using the following measures:

The following physiological measures will be collected and entered directly into REDCap by the interviewer:

- 1) Expired breath carbon monoxide (CO) levels will be assessed using a smartphone-compatible smokerlyzer (remote collection) or lab smokerlyzer (curbside collection), a reliable and valid measure of recent smoking.
- 2) Blood pressure and heart rate will be measured using an automated blood pressure monitor to help the licensed medical professional determine final participant eligibility. The research staff will also submit a Medical Event Form for the licensed medical professional to review along with a Blood Pressure and Heart Rate Symptom Checklist to ascertain details of the symptomatology for the licensed medical professional to review. In severe cases, the licensed medical professional may also choose to call the participant to follow-up and/or withdraw the participant from the study if necessary.
- 3) Urine cotinine will be collected to verify the participant's smoking status. It will be measured using urinary cotinine test strip.

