Product that will be given to participants for the Baseline 2 visit cannot be given/sent to participants until 7 days have passed following completion of the Baseline 1 visit. We will need to calculate baseline smoking rate during this 7-day period and so participants cannot have access to any study product before this 7-day period has ended.

Visit scheduling requirements for baseline period:

Participants will be required to schedule the Baseline 1 visit within 30 days of the completion of their screening visit. If a participant still wants to be in the study after 30 days, she will need to be re-screened. The participant will need to be re-consented but will maintain the original REDCap Subject Identifier. The ideal target window separating Baseline 1 and Baseline 2 is between 7 and 12 days. The minimum is 7 days and the maximum is 21 days. If the participant does not complete the visit within 21 days, then she will not be rescheduled and will be discontinued from the study.

Measures/Assessments

The following physiological measures will be collected at Baseline 1 and recorded directly into REDCap by the interviewer:

- 1) CO
- 2) Blood pressure
- 3) Heart rate

The following assessments will be administered as an interview at Baseline 1 and entered directly into REDCap by the interviewer:

- 1) Concomitant Medications Form
- 2) Time Since Last Cigarette Questionnaire
- 3) Health Changes Questionnaire, which will assess any weekly health changes
- 4) Maintenance Drug Dose Questionnaire (if applicable)

The following assessments will be administered at Baseline 1 and completed by the participant directly in REDCap:

- 1) BDI
- 2) OASIS
- 3) Perceived Health Risks Rating (Hatsukami et al., 2010), a measure of the perceived addictive potential and other health risks associated with cigarettes
- 4) Respiratory Health Questionnaire, a measure of cough, shortness of breath and other respiratory symptoms
- 5) Minnesota Nicotine Withdrawal Scale (MNWS; Hughes & Hatsukami, 1986), a measure of nicotine withdrawal
- 6) Questionnaire of Smoking Urges-brief scale - Usual Cigarette (QSU-brief; Cox, Tiffany, & Christen, 2001; Tiffany & Drobes, 1991), which measures the urge to smoke
- 7) Cigarette Evaluation Scale – Usual Cigarette (CES; Westman, Levin, & Rose, 1992), which measures responses to cigarettes (e.g., reward, satisfaction)

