The sponsors (NIDA/FDA) as well as the Institutional Review Board and regulatory authorities could be granted direct access to original medical and research records for verification of clinical trial procedures and/or data. If this is required, it will be done under conditions that will protect privacy to the fullest extent possible consistent with laws relating to public disclosure of information and the law-enforcement responsibilities of the agency.

Data Storage:

Data will be stored locally for at least 7 years after study completion at the University of Vermont.

Adverse Events

The research assistant will ask about adverse events at each visit during the study, using a form that assesses the nature, severity, duration, action taken, and outcome of study-related adverse events. AEs will be captured from the time of study consent. Participants will be given contact cards to inform us of events that occur between study contacts. Any AE that remains open will be reviewed and closed at the study completion date (completers, withdrawn, etc.)

All procedures will be monitored to ensure that they conform to the approved protocol. In addition, monitoring will be done of all unforeseen circumstances that might arise and affect safety; of all reports of serious adverse events as defined in 38 CFR 46 (death, new or prolonged hospitalization, persistent or significant disability/incapacity); of other significant adverse events (adverse events that lead to drop out by the participant or termination by the investigator); of unexpected adverse events resulting from the study, and of expected adverse events.

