### **5.3. Safety Population**

All participants receiving any study cigarettes will be included in the safety population. Participants who may have attended the screening and first baseline visit, and have been randomized, but did not actually receive any cigarettes will be excluded from the

safety population.

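### Adverse events are tabulated by condition with no onset cut-off, and event counts divided by women are labelled a percent

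*SAP*

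**What the plan says.** The Protocol (Adverse Events) states that "AEs will be captured from the time of study consent". In Study 2, consent is given in the first portion of screening, where "documentation of the participant's informed consent via electronic signature on REDCap will be required prior to participating" (Study 2, Informed Consent Process).

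Study product comes later. Under Study 2 Baseline Procedures, the seven days after Baseline 1 are used to measure baseline smoking, and "participants cannot have access to any study product before this 7-day period has ended". On the interval between the two baseline visits the Protocol says: "The minimum is 7 days and the maximum is 21 days". Its preferred interval is 7 to 12 days. SAP sections 5.1 and 7.2.3 confirm that cigarettes are handed over at the second baseline visit.

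SAP section 5.3 defines who is counted: "All participants receiving any study cigarettes will be included in the safety population". SAP section 8.1 gives event frequencies overall and by condition. For event types, "the percent of adverse events will be computed with the denominator being the number of participants in the safety population", and the next sentence describes the result as events per person. Severity, relatedness and expectedness are also to be given as the frequency and percent of participants. Event type is not. I found no definition of a treatment-emergent event, and no onset cut-off, in either document.

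**The concern.** Two features of the table make it harder to read.

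- **Timing.** The safety population restricts which women count, not which of their events count. Read literally, an event during screening or the baseline week is credited to the condition the woman is assigned later. Until Baseline 2 every participant smokes her own brand, so such an event in the VLNC arm arose under the comparator's exposure. These events can be recorded: the Protocol's section on withdrawal or monitoring calls for a Medical Event Form when blood pressure or heart rate stays out of range at any time after consent.
- **Unit.** Events divided by women is a mean count, not a percentage. It can pass 100%, and one woman with recurrent events adds to it several times. A reader of the by-type table cannot tell how many women were affected.

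SAP section 8 limits reported safety data to adverse events and birth outcomes. These tables are therefore a main source of maternal safety information for the DSMB and the IRBs.

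**Working it through.** The documents give no adverse event rate and no planned precision for the safety comparison, so there is no figure of theirs to reproduce.

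**Inputs**
- Baseline 1 to Baseline 2: minimum 7 days, preferred 7 to 12, maximum 21 (Protocol, visit scheduling for the baseline period).
- End of screening to Baseline 1: "Participants will be required to schedule the Baseline 1 visit within 30 days of the completion of their screening visit".
- Screening itself: "A participant must complete her two-part screening session within 30 days of completing the pre-screening questionnaire".
- Time on product: 12 weeks plus the abstinence visit the next day, 84 + 1 = 85 days (SAP section 4.1).
- True on-product rate ratio (RR): not given; 1.5 and 2.0 are assumed.
- Background event rate: not given; assumed constant, equal in both arms before product, and equally well ascertained before and after product.

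**Step 1: dilution.** With *d* pre-product days, the pre-product share of observation time is d/(d + 85). The expected observed ratio is (d + RR × 85)/(d + 85).

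| d (days) | Share | True 1.5 shows as | True 2.0 shows as |
|---|---|---|---|
| 7 | 7/92 = 8% | 134.5/92 = 1.46 | 177/92 = 1.92 |
| 12 | 12/97 = 12% | 139.5/97 = 1.44 | 182/97 = 1.88 |
| 21 | 21/106 = 20% | 148.5/106 = 1.40 | 191/106 = 1.80 |

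The first two rows cover only the preferred interval between baseline visits. Time from consent to Baseline 1 adds to *d*, but its usual length is not given. The outer limit of the three windows is 30 + 30 + 21 = 81 days (81/166 = 49%). It is reached only if every window is used in full.

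**Step 2: the difference.** The expected number of pre-product events per woman is the same in both arms, so it cancels from the difference in events per woman. Its variance does not cancel. With Poisson counts and equal rates, the variance of the difference rises by (d + 85)/85: 92/85 = 1.08 at 7 days and 97/85 = 1.14 at 12 days. The standard error rises by about 4% and 7%.

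**Step 3: the unit.** Let *m* be the mean number of events per woman and *k* an assumed negative-binomial clustering parameter, from 0.5 (strong clustering) to the Poisson limit. The share of women with at least one event is 1 − (1 + m/k)^(−k), which tends to 1 − e^(−m) for Poisson.

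| m | SAP percent | Women with at least one event (k = 0.5 to Poisson) |
|---|---|---|
| 0.5 | 50% | 29% to 39% |
| 1 | 100% | 42% to 63% |
| 2 | 200% | 55% to 86% |

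**The case against.** The strongest reply is that these are descriptive tables with a disclosed unit. SAP section 8.1 says openly that the result is events per person, plans no adverse event ratio or test, and gives percent of participants for three classifications. Serious adverse events and birth outcomes are separate safety endpoints, and the DSMB may ask for raw data. All of this stands. It limits the consequence, but it supplies neither an onset rule nor a by-type count of women.

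The assumption of equal ascertainment is also open to challenge. The Medical Event Form is listed at the experimental and abstinence visits but not at Baseline 1 or Baseline 2, and the Protocol describes the adverse event form as covering study-related events. Fewer pre-product events may therefore be recorded than Step 1 assumes. Neither point is a time restriction, however, and the Protocol also says that events are asked about at each visit.

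Three stronger readings are tempting, and the documents do not support them.

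- A reader might infer that the safety comparison as a whole is biased towards no difference. Only a ratio is attenuated; the difference is unbiased in expectation.
- A reader might add up the maximum visit windows and conclude that a third to a half of tabulated events precede product. Those are scheduling limits, not expected timing.
- A reader might suppose that a woman with a problem at each of 12 weekly visits adds 12/53 = 23 percentage points to her arm (106 randomised, 53 per arm). The Protocol records duration and keeps unresolved events open until they are closed, so a continuing problem should be one record. Only genuine recurrences count again.

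**Conclusion.** The point holds as a defect of tabulation. Followed literally, SAP section 8.1 credits pre-exposure events to an arm and reports as a percent a quantity that can exceed 100. Over the preferred baseline interval the effect on a ratio is small: a true 2.0 shows as 1.92 to 1.88, with 8% to 12% of observation time before product. This rests on a constant event rate and equal ascertainment, which the documents do not establish. It would be larger with longer screening and smaller if few baseline events are recorded. The labelling problem does not depend on those assumptions, although the sizes in Step 3 rest on assumed means and clustering. No hypothesis test or error rate is affected. The change is worth making because the tables inform maternal safety in a small trial and the correction is cheap.

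**What to change.** In SAP section 8.1:

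1. Base the by-condition tables on events with onset on or after the date the woman first received study product (Baseline 2).
2. List events from consent to that date separately, pooled over conditions.
3. For each event type, report by condition the number and percent of women with at least one event, with the event count beside it. If a rate is wanted, give events per person or per person-week and do not call it a percent.

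The cost is SAP wording and minor table work. One item needs confirming first: the Protocol says the adverse event form assesses duration but does not name onset date, so the team should check that onset is recorded or can be derived.

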The 2009 Family Smoking Prevention and Tobacco Control Act (FSPTCA) gives the Food and Drug Administration (FDA) regulatory authority over tobacco products, including nicotine levels in cigarettes. That is an exciting development as it creates the opportunity to examine the Benowitz and Henningfield (1994) hypothesis that smoking prevalence, nicotine dependence, and smoking-related morbidity and mortality can be lowered substantially by reducing the nicotine content of cigarettes to non-addictive levels. Computer modeling predicts that reducing nicotine levels in cigarettes would produce substantial improvements in population health (Tengs et al., 2005). An essential initial step towards the implementation of such a policy is to thoroughly investigate its safety and potential unintended adverse consequences. Indeed, the FDA's Center for Tobacco Products seeks to establish research centers to assist with the mission of investigating such regulatory matters related to the FSPTCA (see RFA-DA-13-003). The FDA explicitly notes that researching tobacco regulatory questions in vulnerable populations is a crosscutting agency priority, listing women of childbearing age (15-44) and pregnant women among the vulnerable populations of interest.

Approximately 23% of U.S. women of childbearing age are regular cigarette smokers, with prevalence being considerably higher among socioeconomically disadvantaged women. Indeed, disadvantaged women are at increased risk for smoking, nicotine dependence, using high nicotine yield cigarettes, and, perhaps most importantly, for smoking during pregnancy. Not surprisingly, disadvantaged female smokers are also at significantly increased risk for smoking-related adverse health consequences, including cervical cancer, thrombosis related to hormone-based contraception, infertility, and early menopause. Specific to smoking during pregnancy, disadvantaged women are at substantially increased risk for catastrophic pregnancy complications, fetal growth restriction, and adverse birth and neonatal outcomes. Studies testing an innovative regulatory strategy of reducing the nicotine content of cigarettes to a non-addictive level (i.e., <0.2 mg nicotine) have shown promising beneficial effects (decreased smoking rate, reduced toxicant exposure, and increased cessation) in the general population of smokers. However, these studies have uniformly excluded vulnerable populations, especially

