 - m. Dreaming or nightmares
 - n. Nausea
 - o. Sore Throat
- 3) Sample Collection: Breath samples to measure cigarette use and urine tests to confirm pregnancy will be carried out. The results of these tests may be upsetting to participants or cause them discomfort.
- 4) Survey Questionnaires: The interview will include questions about medical and psychiatric history and questionnaires about mood. Answering these personal questions could make the participants feel uncomfortable. Participants can choose not to answer any questions that make them uncomfortable. If a participant reports thoughts of killing themselves or other indicators of suicidality, a study clinician will speak with them. They may also request to talk with a study clinician if they are in discomfort and would like help and/or referrals for mental health resources.
- 5) Exacerbation of psychiatric symptoms: Smoking and nicotine can affect a person's mood and emotions and are associated with psychiatric disorders including major depressive disorder, general anxiety disorder, bipolar disorder and eating disorders. Any changes in nicotine or cigarette consumption could adversely affect psychiatric conditions.
- 6) Obtaining blood pressure: The blood pressure cuff may cause minimal discomfort. In obtaining blood pressure, researchers may find the participant has abnormal blood pressure. If a participant's blood pressure is abnormal, we will inform them of this and may advise them to see a doctor. Our licensed medical professional may also contact them.
- 7) Changes in blood pressure and/or heart rate: Smoking and nicotine can affect the cardiovascular system which may result in changes in blood pressure and/or heart rate.
- 8) Breach of Confidentiality: The risk of the interview is loss of privacy if other people find out the results.

9) Undue Influence: Undue influence is a possible risk due to monetary compensation for participating in the study. The likelihood of this risk is low because the compensation is commensurate with the amount of time and effort required for these studies.

Expected benefits of participation:

There are no immediate benefits from participating in the study. The information obtained from this study may ultimately help the Food and Drug Administration decide how best to regulate tobacco products with the goal of improving public health.

Protection Against Risk

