- 7) Measures of intention to quit: Stages of Change, Contemplation Ladder
- 8) Measures of compensatory smoking: puff topography, filter analysis (Study 1 only)
- 9) Measures of other tobacco use: TLFB-other tobacco
- 10) Measures of cigarette characteristics: CES, CPT
- 11) Measures of cognitive function: BRIEF-A, EQ-5D, TPQ, D-KEFS, WASI-II, DDT, SST (Study 1 only)
- 12) Measures of cardiovascular function: heart rate, blood pressure, urine 11-dehydroTXB2
- 13) Measures of perceived risk: Perceived Health Risk Questionnaire
- 14) Safety outcome variables: Adverse Events (AEs), Serious Adverse Events (SAEs)

References

Alessi, S. M., Badger, G. J., & Higgins, S. T. (2004). An experimental examination of the initial weeks of abstinence in cigarette smokers. *Experimental and Clinical Psychopharmacology*, 12, 276-287.

Alsop, D. C., & Detre, J. A. (1996). Reduced transit-time sensitivity in noninvasive magnetic resonance imaging of human cerebral blood flow. *Journal of Cerebral Blood Flow and Metabolism*, 16, 1236-1249.

Ananth, C. V., Smulian, J. C., & Vintzileos, A. M. (1999). Incidence of placental abruption in relation to cigarette smoking and hypertensive disorders during pregnancy: A meta-analysis of observational studies. *Obstetrics & Gynecology*, 93, 622-628.

Army Individual Test Battery. (1944). *Manual of Directions and Scoring*. Washington, DC: War Department, Adjutant General's Office.

Bakketeig, L. S., Jacobsen, G., Hoffman, H. F., Lindmark, G., Bergsjø, P., Molne, K., & Rødsten, J. (1993). Pre-pregnancy risk factors of small-for-gestational age births among parous women in Scandinavia. *Acta Obstetrica et Gynecologica Scandinavica*, 72, 273-279.

Beck, A. T., Steer, R. A., & Carbin, M. G. (1988). Psychometric properties of the Beck Depression Inventory: Twenty-five years of evaluation. *Clinical Psychology Review*, 8, 77-100.

Beck, A. T., Ward, C., & Mendelson, M. (1961). Beck depression inventory (BDI). *Archives of General Psychiatry*, 4, 561-571.

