## **13. Summary of Changes to the Protocol**

No changes to the analyses outlined in the protocol are proposed in this document.

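### SAP 8.1 limits the by-condition adverse event results to oversight bodies, and no SAP section summarises heart rate or blood pressure, although the protocol lists both sets of outcomes as Study 2 secondary endpoints

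*SAP*

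**What the plan says.** **Adverse events.** SAP 8.1 describes frequencies of adverse events overall and by condition, with the safety population as denominator. It classifies them by MedDRA category, severity, relatedness and expectedness. It then says: "Safety analyses will be reported only to the DSMB and the appropriate Institutional Review Boards". The same sentence makes one exception: serious events go to the sponsor as well. SAP 8 opens with: "Adverse events and birth outcomes will be the only safety data that will be reported".

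**Heart rate and blood pressure.** In the protocol's Outcome Variables, under the secondary endpoints for both studies, item 12 reads "Measures of cardiovascular function: heart rate, blood pressure, urine 11-dehydroTXB2". Item 14 lists adverse and serious adverse events as the safety outcome variables. Items 4, 8 and 11 of that list are marked as applying to Study 1 alone; items 12 and 14 are not. Potential Risks of Participation, item 7, states: "Smoking and nicotine can affect the cardiovascular system which may result in changes in blood pressure and/or heart rate". The Study 2 visit schedules list both measures at screening, both baselines, every weekly visit and the abstinence session.

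In the SAP, heart rate and blood pressure appear only in section 5, as eligibility limits. They are absent from the endpoint lists (6.1, 6.2, 6.4), from the secondary analysis (7.4) and from section 8, where 8.3 (other safety measures) is marked as not applicable. SAP 13 says: "No changes to the analyses outlined in the protocol are proposed in this document".

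**The concern.** There are two separate problems.

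The first is where results go. The by-condition adverse event tables are planned, but the SAP names a closed list of recipients that does not include the trial's own report. A team following it literally could publish the smoking-rate result with no adverse event comparison beside it.

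The second is a listed endpoint with no analysis. Heart rate and blood pressure are collected throughout, yet no table is specified. A modest difference between conditions that stays within the permitted range would not be looked for.

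Both matter because the population is pregnant women, in whom the protocol says there were no empirical data on these cigarettes. Its Background also says that, before a nicotine-reduction policy is implemented, one must "thoroughly investigate its safety and potential unintended adverse consequences".

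**Working it through.** The plan gives no figure to reproduce. The check compares the texts and counts visits.

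**Step 1: adverse events, protocol against SAP.**
- Protocol, Outcome Variables, item 14: adverse and serious adverse events are a secondary endpoint for Study 2.
- SAP 6.4 and 8.1: they are an endpoint, and by-condition tables are planned. The analysis exists.
- SAP 8.1, recipients: DSMB and IRBs, plus the sponsor for serious events.
- Other routes in the protocol: serious events are summarised yearly to the funding agency (Adverse Events section). DSMB meeting reports go to the IRBs and the funder's program officer, and the FDA is told of significant action arising from DSMB findings (DSMB section).

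All of these are oversight routes. None places adverse events by condition in the trial's results. SAP 8.1 also says birth outcomes will be described but not to whom. They are safety endpoints in SAP 6.4, so it is unclear whether the same restriction covers them.

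**Step 2: heart rate and blood pressure, visit count in Study 2.**

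| Visit | Occasions |
|---|---|
| Screening | 1 |
| Baseline 1 and 2 | 2 |
| Weeks 1, 3, 5, 7, 9, 11 | 6 |
| Weeks 2, 4, 6, 8, 10, 12 | 6 |
| Abstinence session | 1 |
| Total | 16 |

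Screening serves eligibility, and both baselines precede use of the assigned cigarettes. The occasions that can show an effect of condition number 16 − 3 = 13. The abstinence session counts for everyone who attends, because the protocol also measures heart rate and blood pressure in women who do not meet the abstinence criterion.

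- Planned readings of each measure: 13 × 90 completers = 1,170.
- Per condition: 13 × 45 = 585.
- Number with a summary or comparison planned in the SAP: 0.

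**Step 3: can the event route stand in for an analysis?** The protocol's Withdrawal or Monitoring section requires a Medical Event Form when a repeat manual reading remains out of range. The form is mandatory at that point, so confirmed abnormal values can reach the adverse event tables. Two limits remain. The route cannot show a shift between conditions inside the permitted range. It also presumes a manual repeat, whereas Study 2 readings are taken over video with an automated cuff; the documents do not say how the two fit together.

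**Step 4: the statement of no change.** SAP 13 refers to analyses outlined in the protocol. The protocol's Study 2 Statistical Methods section names no heart rate, blood pressure or adverse event analysis specifically. It does give general summaries for continuous outcomes and an adjusted secondary analysis for all outcomes. SAP 13 is therefore not plainly false, but it leaves the loss of item 12 undeclared.

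**The case against.** The strongest reply has four parts.

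1. **The protocol itself classes heart rate and blood pressure as cardiovascular function, not safety.** SAP 6.4 and 8 match the protocol's own safety definition and add birth outcomes. This stands. A reader might infer that SAP section 8 contradicts the protocol, but the gap lies mainly in SAP 6.2 and 7.4.

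2. **The endpoint list is shared by two studies and may be stale.** It includes NNN, minor alkaloids and urine 11-dehydroTXB2, none of which is in the Study 2 specimen plan (NNAL, PAH and cotinine). This is a fair explanation for part of the list. It is weaker for heart rate and blood pressure, which Study 2 does measure at every visit, and three other items were marked as Study 1 alone. In either case the documents need reconciling.

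3. **Safety information does reach others.** The sponsor receives serious events, and the other oversight routes are set out above. This stands, so it would be wrong to infer that nothing leaves the DSMB and IRBs. It does not supply a by-condition report.

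4. **The sentence may describe only reporting during the trial, and the opening of SAP 8 could imply that adverse events are reported generally.** That is possible, but the wording sets no such limit, and the two sentences then need to be made consistent.

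**Conclusion.** The point holds in two parts. The recipient wording in SAP 8.1, read literally, excludes adverse events by condition from the trial's reported results. Heart rate and blood pressure, listed as Study 2 secondary endpoints, have no planned summary in the SAP: 13 occasions per completer, about 1,170 planned readings of each for 90 completers. That count assumes every visit is attended. Missed weekly visits are not made up, which lowers it; data from women who do not complete would add to it. It measures data left unused, not the size of any effect.

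Stronger readings are not supported. A reader might infer that adverse events go unanalysed, but by-condition tables are planned and only their destination is at issue. A reader might infer that abnormal readings are lost, but a confirmed one requires a Medical Event Form. Nor do the documents make safety the trial's main purpose: Study 2's primary aim is smoking rate, and the Background passage on safety concerns what should precede a policy. The primary analysis is untouched, so this should be corrected but does not threaten the main result.

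**What to change.** 1. **SAP 8.1:** delete the word that restricts the recipients. State that adverse and serious adverse events by condition form part of the trial's reported results as well as going to the DSMB, the IRBs and the sponsor. Say the same for birth outcomes, or say where they go.
2. **SAP 6.2 and 7.4:** add heart rate and blood pressure. Use the repeated-measures model already specified, with baseline as a time point, so that the condition-by-visit term gives the change from baseline by condition. Take baseline as the mean of the two baseline visits, as the protocol's Study 2 methods provide. Treat the abstinence session separately, as SAP 7.3.1 does for craving and withdrawal.
3. **One further table:** the number of women in each condition with a confirmed out-of-range reading, using the limits and repeat-reading step already in the protocol's Withdrawal or Monitoring section. The sponsor should reconcile that section's manual repeat with the remote automated readings, so that a confirmed reading can be identified in the data.
4. **Alternative to 2 and 3:** if item 12 is not meant for Study 2, declare and justify dropping it in SAP 13.

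The cost is SAP wording and two tables from data already in REDCap. No new collection is needed.
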